1.7 Drugs/Devices/Biologics

We will treat HDs and MS patients with HFS consisting of a mixture of soluble (inulin and fibersol-2) and insoluble (oat bran, corn bran, wheat bran and sorghum bran) fibers. MS patients will consume HFS as drink to achieve a dietary fiber intake of > 60 g/day for 12 weeks.

The HFS that will be used in this study is a mixture of brans and xanthan gum (49.8% oat bran, 12.8% corn bran, 18.7% sorghum bran, 14.8% wheat bran and 4% xanthan gum w/w). The brans are the major ingredients in the wholegrain, traditional Chinese medicinal foods and prebiotic (WTP) diet that we used in reference #4 and therefore the HFS also contains a large amount of fiber of diverse physicochemical structures. This high fiber supplement has been tested in a clinical study approved by the New Brunswick/Piscataway Arts and Sciences Institutional Review Board of Rutgers University (protocol # 18-074m) and registered on ClinicalTrials.gov (NCT03334643). We showed that the HFS was well-tolerated and induced minimal changes in blood glucose in individuals who had normal glycemic control, prediabetes or type 2 diabetes. A sample of the HFS was tested for nutrient profiling, microbial load check, and stability and shelf life by an ISO 17025 accredited food nutritional laboratory (Eurofins Nutrition Analysis Center). The supplement will be produced in large quantities by an industrial partner (a food ingredient supplier). The supplement will be stored at a food-grade facility. The supplement will be contracted to a food company to be produced in large quantities and packaged into sachets (one sachet per fiber drink) by an industrial partner (a food ingredient supplier). A nutritional label will be printed on the sachets.

1.8 Specimen Collection

A. Primary Specimen Collection

A. *What types of specimen will be collected, where, and by whom?*

1. Blood specimen will be collected by [name], APN at RWJ MS center (Rutgers-Robert Wood Johnson Medical center at [name]).

All subjects (MS patients and healthy donors) will have 3 blood samples collected at baseline, 8 weeks and 12 weeks. The amount of each blood sample will be approximately 80ml.

For subjects with MS who experience a relapse, there will be 2 more blood samples that pertain to the relapse. The first blood sample will be collected during the acute phase of the MS relapse and the second blood sample will be drawn once the patient has recovered from the symptoms of the relapse. This second blood sample can range anywhere from 1-6 months and will be at the discretion of the PI, [name].

2. Fecal samples will be collected by participants at home. There will be 3 fecal samples collected at baseline, 8 weeks and 12 weeks.

For subjects with MS who experience a relapse, there will be 2 specific fecal samples that pertain to the relapse. The first fecal sample will be collected during the acute phase of the MS relapse and the second fecal sample will be collected once the patient has recovered from the symptoms of the relapse. This second fecal sample can range anywhere from 1-6 months and will be at the discretion of the PI, [name].

If an enrolled MS participant has a flare up during or after study completion, they will be asked to participate in this MS relapse group (Group E) and have 2 additional blood samples and 2 additional stool samples collected. They will be asked to sign the MS relapse consent form.

B. How will the specimens be transported and by whom?

1. Blood will be transported to the laboratory (Department of Neurology, [name]) from RWJ MS center in New Brunswick in a private vehicle by [name] [name] (IATA Refresher Completed 8/23/21) or [name] (IATA Refresher Completed 10/12/19).
2. Fecal samples will be transported by study participants to our laboratory in Piscataway (Department of Neurology, [name]), and received by [name] [name]. If the study participants cannot transport the fecal samples, [name] [name] or [name] will pick up the fecal sample at their home.

C. Who will process the specimens?

Blood and fecal samples will be processed by [name] and [name]. Aliquots of the fecal samples will be further processed for 16S rRNA gene sequencing by graduate student [name] in [name] laboratory:

**[name]
[name].**

D. How long will the specimens be kept?

Kept in a -80°C freezer for 3 years.

The morning of the scheduled visit, subjects will be asked to collect a single-stool sample using a special container. The container containing the stool sample will be then placed in a plastic bag containing a disposable oxygen-absorbing /carbon dioxide-generating packet and then placed in an airtight box with ice packs. The container, ice packs, a disposable oxygen-absorbing /carbon dioxide-generating packet and box will be provided to each subject prior to stool collection. The collected stool sample will be brought to the MS research laboratory at Piscataway by a patient. If MS patient cannot bring the stool sample to the MS research laboratory, our lab staff will pick up the stool sample. Enough ice packs will be provided to preserve the stool in the event of delay during transport.

E. How will the specimens be destroyed upon study completion?

By autoclave.

F. If specimens will be banked for future use, what will be the process for providing investigators with access to the bank and how will this be tracked?

Frozen specimens will be stored at -80°C freezer and the specimens will be tracked by [name] computer.

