These 25 subjects will be those participants with MS who are already part of the above study (Group A or B) and consent to 2 extra blood and 2 extra fecal samples collected at the time of the acute flare up and upon resolution of symptoms. These subjects will be asked to sign a separate consent form agreeing to be part of the MS flare up group (n=25). Since around 50% of RRMS patients relapse at least once per year, we anticipate recruiting 25 relapsing RRMS patients from Group A and B in 1 years (2). RRMS flare up and resolution will be determined by [name].

Table-1. Schedule of specimen collection

Screening/Baseline assessment	8 weeks post HFS	12 weeks post HFS	Unscheduled visit at MS Relapse	Unscheduled visit at MS remission
MS history Medical history Medication history Food Allergy Consent Blood draw* Fecal collection*	Blood draw Fecal collection	Blood draw Fecal collection	Blood draw** Fecal collection**	Blood draw Fecal collection

--	--	--	--

*Sample collection will be done on the day of screening or before high fiber supplement.

** Sample collection will be done at MS relapse before steroid treatment.

Sample collection:

1. Stool Sample: Subjects will be asked to collect a single-stool sample without any laxative or dietary restrictions using a sample collection kit (Appendix 1). The collected stool sample will be brought to the MS research laboratory by the participants. If participants cannot bring the stool sample to the MS research laboratory, our lab staff will pick up the stool sample. The stool sample will be examined for the composition of gut bacteria. The stool sample will also be transplanted into an animal model of MS and examined for the development of experimental autoimmune encephalomyelitis (EAE).

2. Blood Draw: All participants will visit RWJ MS center to provide a blood specimen. Each subject will have a blood draw (80ml – about 5 tablespoons) as shown in Table-1. The immune cells will be isolated from each blood specimen and the presence of pathogenic and regulatory immune cells will be analyzed.

*NOTE: It is requested that all blood work be fasting. Nothing to eat or drink 10-12 hours before blood draw. Subjects may have water &/or black coffee /tea.

Fasting is very important to check the levels of short-chain fatty acid in the serum.

B. Experiment

1. Examine the effect of HFS on production of SCFA, intestinal microbial composition, and intestinal permeability

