We will also examine the development of inducible EAE in C57BL/6 mice transplanted with fecal samples. Germ-free C57BL/6 mice will be purchased from Taconic Inc. and expanded for the experiment. The fecal samples will be collected from regular diet- and HFS-treated HDs and MS patients as described above and transplanted into the germ-free C57BL/6 mice (10 in each group). The transplanted mice (7-9 week-old) will be immunized with MOG35-55 at 200 ug/mouse and injection with pertussis toxin at 100 ng/mouse. Development of EAE will be examined for 40 days. Demyelination and axonal loss in the brain and spinal cord will be examined by immunohistology

with anti-MBP and -Neurofilament Abs, respectively. Microbial composition, intestinal permeability, and development of Th-1, Th-17, Th-GMCSF and Foxp3 Tregs will be examined as described above.

3. Explore biomarkers of MS-associated gut dysbiosis and response to HFS:

RR-MS and healthy donors (21-55 year-old) from RWJ MS Centers will be asked to participate in this study according to institutional IRB guidelines. In this study, fecal and blood samples will be collected from RR-MS patients during relapse (before steroid treatment) and later during remission and examined for intestinal inflammation, permeability and microbial composition. We will enroll 25 patients based on sample size calculation using related previous studies with a statistical power of 80% (8, 20). The fecal samples (200 mg) will be dissolved in 0.5 ml PBS containing proteinase inhibitor and the supernatant will be collected. The concentration of intestinal inflammation biomarkers including Lcn-2, Calprotectin, and Lactoferrin, and a biomarker for intestinal permeability, serum zonulin, will be measured by ELISA assay. We will examine the association between increase in intestinal inflammation/permeability and disease activation.

The fecal samples collected from HFS-treated and un-treated MS patients at the 3 time points described in Aim-1, will be analyzed for intestinal inflammation and permeability as described above. We will simultaneously examine the microbial composition in the fecal samples as described in Aim-1 to determine if an association between MS relapse and gut dysbiosis exists.

C. Study Duration

Subjects participation will be 12-week period.

Study Timetable:

Upon IRB approval-Sept. 2023 Collection of blood and fecal specimens

Sept. 2021-Sept. 2023 Analysis of blood and fecal specimens

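### In Experiment 3 the relapse-to-remission change mixes resolution with steroid exposure and elapsed time; record both and add a second within-patient contrast

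*Combined protocol and SAP*

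**What the plan says.** Section 1.3 B, Experiment 3, states that "fecal and blood samples will be collected from RR-MS patients during relapse (before steroid treatment) and later during remission". Stool is assayed for Lcn-2, calprotectin and lactoferrin, and serum for zonulin, to see whether higher values go with disease activation. The secondary endpoint (1.3 D) is biomarkers of exacerbation.

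- **First sample.** The Table 1 footnote says "Sample collection will be done at MS relapse before steroid treatment".
- **Second sample.** Section 1.8 A says "the second blood sample will be drawn once the patient has recovered from the symptoms of the relapse". It then adds "This second blood sample can range anywhere from 1-6 months and will be at the discretion of the PI" and, for stool, "This second fecal sample can range anywhere from 1-6 months and will be at the discretion of the PI". It does not say from what date the interval runs.
- **Who decides.** Section 1.3 A gives the judgement of both flare and resolution to one person and lists no criteria.
- **Who is sampled.** Group E is drawn from Group A (HFS for 12 weeks) and Group B (no HFS). Section 1.8 A allows entry "If an enrolled MS participant has a flare up during or after study completion".
- **What is recorded and analysed.** Table 1 lists medication history at screening/baseline only; its relapse and remission columns list blood and stool alone. Section 1.9 (Data Collection) is marked not applicable, and heading 6.1 (Data Analysis) has no text under it.
- **Comparison groups.** Section 1.6 A names two groups for Experiment 3: MS patients in relapse and healthy volunteers.

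**The concern.** By taking the first sample before steroids, the plan treats steroids as something that could disturb these markers. The second sample has no matching protection. It comes after whatever treatment the relapse received, at an interval that varies and that the investigator chooses. If a marker falls between the two, the fall could reflect resolution, the steroids or the passage of time. Nothing that the plan lists for collection or analysis would tell these apart.

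At stake is the reading of the secondary endpoint. A fall from relapse to remission is the most natural evidence for a marker of exacerbation, and here it would be ambiguous.

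**Working it through.** **1. The plan's own figures.** Section 1.3 A expects 25 relapsing patients in a year: 50 × 0.50 = 25, which reproduces. The 80% power claimed for 25 patients cannot be reproduced, because no effect size, SD or test is given. If the test is paired (normal approximation, two-sided 5%), it implies (1.960 + 0.842)/√25 = 0.56 SD of the paired difference.

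**2. The two samples side by side.**

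| | Relapse sample | Remission sample |
|---|---|---|
| Steroids for that relapse | not yet given | already given, where used |
| Timing | acute phase | after recovery, 1–6 months, investigator's choice |
| HFS, Group A | on or off | mostly off |
| HFS, Group B | never | never |
| Steroid or HFS status listed in Table 1 | no | no |

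Steroids can differ in any pair where they are given. Elapsed time differs in every pair.

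**3. How many pairs change HFS status from relapse to remission?** Assume a constant hazard matching the protocol's 50% per year, so the chance of relapse by week w is 1 − 0.5^(w/52).
- During 12 weeks of HFS: 1 − 0.5^(12/52) = 0.148, and 25 × 0.148 = 3.7 Group A patients.
- Assume relapse times uniform over 12 weeks and delays uniform over 1–6 months (4.345 to 26.07 weeks). The share still on HFS at remission is (12 − 4.345)²/2 ÷ (12 × 21.725) = 29.3/260.7 = 0.11, so 0.89 have stopped.
- Pairs affected: 0.89 × 3.7 = 3.3. At 30% to 70% per year the figure is 1.8 to 5.4.

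**4. Would the last scheduled sample be a cleaner reference?** It precedes that relapse's steroids, and the investigator does not choose its date. HFS status in Group A is a problem, however. Over one year, with the same hazard:

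| Relapse occurs | Expected of 25 | Reference | HFS at reference → relapse |
|---|---|---|---|
| Before Week 8 | 25 × 0.101 = 2.5 | Baseline | off → on |
| Weeks 8–12 | 3.7 − 2.5 = 1.2 | Week 8 | on → on |
| After Week 12 | 12.5 − 3.7 = 8.8 | Week 12 | on → off |

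So 2.5 + 8.8 = 11.3 of 12.5 Group A pairs change status (6.9 to 15.7 pairs at 30% to 70% per year). Pairs with unchanged status are 12.5 from Group B plus 1.2 from Group A, or 13.7. At 30% per year they would be 7.5 + 0.6 = 8.1.

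**5. Illustration of the consequence.** Take a paired t-test with n = 25, two-sided 5%, no relapse effect, and a shift δ (in SDs of the paired difference) from steroids or time. The noncentrality is δ√25 on 24 degrees of freedom.

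| Assumed δ | Noncentrality | P(p < 0.05) |
|---|---|---|
| 0 | 0 | 0.05 |
| 0.2 | 1.0 | 0.16 |
| 0.3 | 1.5 | 0.30 |
| 0.5 | 2.5 | 0.67 |

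The documents give no value for δ and name no test.

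**The case against.** The strongest case against runs as follows. Recovery time varies, so some flexibility is unavoidable, and the investigator's discretion is tied to symptom recovery. The documents do not say that every relapse is treated with steroids, and nothing in them shows a steroid effect on these markers lasting 1–6 months. Section 1.6 A defines Experiment 3 as relapse versus healthy volunteers, where the relapse sample precedes that relapse's steroids. The scheduled samples are not ignored either: section 1.3 B assays them for the same inflammation and permeability markers. The aim is secondary and exploratory.

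Much of this stands, and it limits the point. A reader might infer that no finding of Experiment 3 could be attributed to disease activity. The documents do not support that, because the healthy-volunteer comparison is untouched by that relapse's steroids. It does not fill the gap, though: it cannot separate being in relapse from having MS, which is what a within-patient contrast is for.

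A reader might also infer that stopping HFS could produce a fall in these markers on the same footing as steroids or time. It affects about 3 pairs. The protocol also hypothesises that HFS reduces dysbiosis, so on its own reasoning withdrawal would tend to raise the markers and hide a fall.

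Finally, a reader might conclude that the pre-relapse sample should replace remission as the main reference. Step 4 argues against this: HFS mismatch would rise from about 3 pairs to about 11. For relapses after Week 12, stopping HFS could then mimic the rise being sought. Nor is the pre-relapse sample assured to be quiescent. The listed eligibility criteria do not exclude a recent relapse or recent steroids, and section 1.4 C reports fecal Lcn-2 rising 3–4 weeks before onset in mice.

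**Conclusion.** The concern holds for one comparison. As written, a relapse-to-remission change in Lcn-2, calprotectin, lactoferrin or zonulin cannot by itself be attributed to resolution, because steroids (where given) and 1–6 months of elapsed time move with it and are neither listed for recording nor handled in any analysis. This follows from the text and rests on no numerical assumption.

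The size of any bias is unknown. The 16% to 67% range shows what assumed shifts would do and is not an estimate of the trial's error rate. The HFS counts assume a constant hazard at the protocol's 50% per year, one year of follow-up, and uniform relapse times and delays. The issue is worth correcting because it bears on the secondary endpoint and the remedy is cheap.

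**What to change.** 1. At the relapse and remission samples, record the date of the last steroid dose (if any), days since relapse onset, and HFS status (on, off, never).
2. Keep relapse versus remission. Prespecify a second within-patient contrast of relapse versus the last scheduled sample before it, using Group B plus only those Group A pairs with the same HFS status at both samples. Report the interval for each pair.
3. Describe a marker as related to exacerbation only if both contrasts point the same way. Otherwise report the relapse-to-remission change as possibly due to steroids or time. Give both estimates with confidence intervals: the contrasts share the relapse sample, so agreement in direction is a minimum check and not a test.

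**Cost.** No new samples and no change to care. Section 5.2 already foresees access to medication records for MS participants, so the added data items are few. The second contrast is small: with 12 to 14 pairs, 80% power needs about 2.80/√12 = 0.81 to 2.80/√14 = 0.75 SD of the paired difference. Some references will be months old. A sample from the 3–4 weeks before relapse may already be raised if the mouse Lcn-2 pattern holds in MS, which is why the intervals must be shown.

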During the baseline visit, all MS patients and HDs will provide a blood and stool sample. For MS patients and HDs who are in the HFS group, they will be provided with supplies and instructions to take the supplement (Appendix 5). All the participants will be provided with stool kits and instruction on stool collection. Stool samples will be collected at home and transported to the laboratory by the participant in Piscataway for analysis.

Group A and Group C: MS patients in Group A and HDs in Group C will consume supplement orally as a drink two times a day to ensure fiber intake of 60 g/day for 12 weeks (High-fiber supplement group, Group A), as shown in [name] T2DM study (1). Participants will gradually increase the dosage of supplement over several days to mitigate the potential tolerability issues,

starting with daily consumption of 30g/day for first 5 days and then increasing to targeted daily consumption of 60g/day.

A member of the research team will follow up by phone at the end of the first week to check for compliance and adverse effects and then every month thereafter (Appendix 6). Patients will receive the fiber supplement in individual sachet (30g/sachet) by mail every two weeks, and they will be asked to return any unused supplement in their next study visit. Since the risks of study drug on embryofetal development are unknown, participants in Group A and Group C will be required to use contraception methods. Please refer section 5 special considerations for more details.

At baseline, Week 8 and week 12, 6 samples (3 blood and 3 fecal sample) will be collected from each subject.

All MS patients will be followed prospectively, and one more blood and one more fecal sample will be collected during relapse (before steroid treatment) and upon symptom resolution, and examined for intestinal inflammation, permeability, and microbial composition. The concentration of intestinal inflammation biomarkers in feces including Lcn-2, Calprotectin, and Lactoferrin, and a biomarker for intestinal permeability, serum zonulin, will be measured by ELISA assay.

As a control we will also analyze these biomarkers in the fecal samples isolated from healthy donors (n=25) in **Group C** and **Group D**. Healthy donors will be asked to provide 3 blood and 3 stool samples over the course of 12 weeks (baseline, week 8, and week 12).

Group E will consist of 25 subjects with MS who experience an MS flare up.

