4.4 Consent Procedures

A. Consent Process

▪ Location of Consent Process

Rutgers – Robert Wood Johnson Medical Group
RMJ Multiple Sclerosis Center,
[name]

▪ Individual Roles for Researchers Involved in Consent

[name] [name] &/ or [name], APN, MSCN (study coordinator) will be the only 2 individuals who will obtain informed consent from study participants.

▪ Consent Discussion Duration

Consent discussion will take place until the subject is fully aware of all study details and all questions have been answered. There is no set time for consent discussion.

▪ Coercion or Undue Influence

Subjects will not be coerced to participate. Participation is voluntary and will not interfere with any current or future medical care at the MS Center.

▪ Subject Understanding

Subjects will be able to read / review the consent in its entirety. Study participation and expectations will be fully and clearly explained. The timeline of study will also be explained. Subjects will have all questions answered prior to signing of the informed consent. Subjects will receive a copy of the signed / dated informed consent.

B. Waiver or Alteration of Consent Process

N/A

C. Documentation of Consent

▪ **Documenting Consent**

The study will be explained to the subject by the investigator and/or study coordinator. The subject will be allowed time to read the consent. All subject's questions will be answered. The subject and investigator and/or study coordinator will sign the consent form. A dated and signed copy will be given to the subject.

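### Relapse-sampling consent is sought only after a flare has begun, although both samples are due before steroids, and the target of 25 leaves no room for missed samples

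*Combined protocol and SAP*

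**What the plan says.** **Consent.** Section 1.8 A makes the flare the trigger: "If an enrolled MS participant has a flare up during or after study completion, they will be asked to participate in this MS relapse group". It adds: "They will be asked to sign the MS relapse consent form". Section 1.3 A confirms that this form is not the main one: "These subjects will be asked to sign a separate consent form agreeing to be part of the MS flare up group". Under section 4.4 A, two named staff "will be the only 2 individuals who will obtain informed consent from study participants". Table 1, however, lists consent only in the screening/baseline column.

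**Timing.** The Table 1 footnote, attached to both blood and stool at the unscheduled relapse visit, reads: "Sample collection will be done at MS relapse before steroid treatment". The text of section 1.3 A agrees and applies it to all MS patients: "one more blood and one more fecal sample will be collected during relapse (before steroid treatment) and upon symptom resolution". Section 1.3 B, Experiment 3, repeats the pre-steroid condition. Section 1.8 A drops it: "The first blood sample will be collected during the acute phase of the MS relapse", with parallel wording for stool.

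**Practicalities.** Stool is collected at home (section 1.8). Kits are handed out at baseline (section 1.3 A), and staff will fetch a sample that the participant cannot bring. No kit is set aside for a relapse. Fasting is requested for all blood work, with no exception for relapse visits: "Nothing to eat or drink 10-12 hours before blood draw". The reason given is serum SCFA.

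**Numbers.** Section 1.3 A expects 25 relapsing patients from Groups A and B in one year, on the basis that around 50% of RRMS patients relapse at least once a year.

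**The concern.** The relapse sample is the one specimen in this study that cannot be scheduled or repeated. Under the plan, the clock starts when the patient reports a flare. From then on, one of two people must take a new written consent, a stool kit must be at hand, and a home stool and a blood draw must both be obtained before any steroid. Consent is the step that could most easily have been done in advance, and it is left until then.

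Two things can go wrong. A pre-steroid sample may be missed. Or a sample taken after steroids may be accepted, because the section 1.8 wording admits it and no rule says how to classify it. The first shrinks Group E. The second mixes steroid-exposed values of Lcn-2, calprotectin, lactoferrin and zonulin into the relapse measurement. Objective 2 and the secondary endpoint rest on these samples, and the planned number has no reserve.

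**Working it through.** **Inputs.** 50 MS patients (section 4.3 A). Around 50% relapse at least once a year, and 25 expected in one year (section 1.3 A). 80% power with 25 patients (section 1.3 B, Experiment 3). n = 20 described as sufficient in the IBD data borrowed for Aim 3 (section 1.5). The share of relapsing patients who consent and give both valid pre-steroid samples, *c*, is not in the documents; it is varied below as an assumption.

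**1. The plan's figure.** 50 × 0.50 = 25. This reproduces the stated target exactly, so refusal, late reporting and missed samples are implicitly set to zero.

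**2. Chance of reaching the target.** Treat patients as independent, each followed for a full year, and let X be the number captured: X ~ Binomial(50, 0.5*c*). At *c* = 1 the distribution is symmetric about 25, so P(X ≥ 25) = 0.5 + 0.5 × P(X = 25) = 0.5 + 0.5 × 0.112 = 0.556.

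| Assumed capture *c* | Expected (25*c*) | P(X ≥ 25) | P(X ≥ 20) |
|---|---|---|---|
| 100% | 25.0 | 56% | 94% |
| 90% | 22.5 | 28% | 80% |
| 80% | 20.0 | 10% | 55% |
| 70% | 17.5 | 2% | 27% |
| 60% | 15.0 | 0.2% | 9% |
| 50% | 12.5 | <0.1% | 1% |

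**3. Cost in power.** The stated 80% cannot be reproduced, because no mean, SD or effect size is given. Instead, take a paired relapse–remission comparison with a normal approximation and two-sided 5% (assumed). The effect with 80% power at n = 25 is (1.960 + 0.842)/√25 = 0.56 SD. At n = 20, power is Φ(0.56 × √20 − 1.96) = 71%; at n = 15 it is 58%.

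Section 1.6 instead describes relapsing patients against healthy volunteers. Take the effect that has 80% power at 20 per group: 2.802 × √(2/20) = 0.886 SD. Against 25 controls, power is 88% with 25 relapsing patients, 84% with 20 and 77% with 15.

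**4. When flares fall.** Section 1.3 C sets participation at 12 weeks, but the forecast covers a year. At a constant relapse rate (assumed), 50 × (1 − 0.5^(12/52)) = 7.4 patients would have a first relapse within 12 weeks. The other 17.6 of the 25 would come later, when kits issued for the three scheduled stools may already be used.

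**5. Texts that do not match.**
- Section 1.3 A has all MS patients sampled at relapse. Later in section 1.3 A, and in section 1.8, sampling depends on a separate consent.
- Table 1 has consent at screening/baseline only. Section 1.8 adds one at the flare.
- Section 1.3 and Table 1 say before steroids. Section 1.8 says acute phase.

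**The case against.** A reader might infer more from this sequence than the documents allow.

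- **That fasting must be met and will cost stool samples.** It is requested, not required. Its stated purpose is serum SCFA, while the serum marker named for the relapse work is zonulin. A blood fast cannot cause a missed stool.
- **That stool and blood must fit into one visit.** Nothing says so; each has only to precede steroids. The documents give no interval between presentation and steroids, so how tight this is cannot be judged.
- **That Group E will favour mild flares that can wait.** The documents have no data on severity, reporting delay or steroid timing. The opposite is also possible: mild flares may go unreported, which would select severe ones.
- **That sampling delays treatment.** No section says this.

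Other points weigh against the concern. Kits at baseline and home pick-up ease stool collection. Relapse has to be determined by the study's own clinician, so contact with the team is built in. One of the two consent-takers is the study coordinator, so a staffing bottleneck is not shown. Flares after study completion are allowed, and one sentence in section 1.3 says Group E can, rather than will, come from Groups A and B, so 25 may be reached over a longer period. Fresh consent for a flare after the 12 weeks is a defensible choice. All MS patients being sampled and a consent condition can be read as procedure plus proviso. In the two-group comparison, falling to 20 costs little power.

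All of this stands and limits the claim. What it leaves untouched is the order of events: consent is sought only after onset, no relapse kit is assigned, one section would accept a post-steroid sample, and the target has no margin.

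**Conclusion.** The concern holds as a feasibility and sample-definition weakness that is cheap to remove. Some pre-steroid relapse samples may be missed, and some post-steroid samples may be counted as relapse values, because consent waits for the flare and section 1.8 omits the steroid condition.

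The target of 25 has no allowance. The chance of reaching it in a year is about 56% with full capture and about 10% at 80% capture, when 20 are expected. These figures assume independent patients, a full year of follow-up for all 50 and the plan's own 50% relapse rate; the 80% is illustrative. Twenty is also the number that section 1.5 calls sufficient, so a modest loss would not by itself defeat the aim.

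The actual loss, and any selection by severity, cannot be determined from the documents and should not be asserted. Nothing here bears on when steroids are given.

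**What to change.** 1. Seek relapse-sampling consent from every MS participant at enrolment, with the right to decline, and reconfirm it at the flare.
2. Give each MS participant a stool kit at baseline that is reserved for relapse.
3. Keep fasting as a request at the relapse draw and record time since last intake, so that unfasted serum SCFA values can be flagged. Dropping the request altogether would sacrifice that measure.
4. Record the date and time of stool, blood and any first steroid dose.
5. Keep post-steroid samples out of the primary relapse value and report them separately.
6. Log all relapses, including those not sampled and the reason, so that the size and pattern of loss can be described.
7. Reconcile the section 1.3 A statement that all MS patients are sampled at relapse with the separate consent in sections 1.3 A and 1.8. Align the consent entry in Table 1 with section 1.8. Reconcile the acute-phase wording in section 1.8 with the pre-steroid condition in section 1.3 and Table 1.

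The cost is a consent-form amendment, up to 50 stool kits and a few extra data fields. No added visits or participants are needed.
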